Oregon Health & Science University RESEARCH PROTOCOL

Protocol Title:

Evaluating Community Health Centers' Adoption of a New Global Capitation Payment (eCHANGE)

Principal Investigator:

[name]

Assistant Professor, Oregon Health & Science University Department of Family Medicine
[name]
[name]

[contact]

Sponsor:

Robert Wood Johnson Foundation, grant #71125
Agency for Healthcare Research and Quality (AHRQ)

Specific Aims:

Aim 1: Assess pre-post Alternative Payment Methodology (APM) changes in internal services utilization and quality of clinical care delivered in intervention sites, as compared with control sites.

Hypothesis 1a: Patterns of internal services utilization (e.g., face-to-face visits, e-mail visits) will change among intervention clinics' patients from pre- to post-APM, while control clinics' patients' rates will not change.

Hypothesis 1b: Intervention site patients will achieve greater pre-post improvements in quality of care delivered internally, as compared to the rates of improvement for patients in control clinics.

Aim 2: Measure pre-post changes in patients' utilization of external services (e.g., emergency department) and overall costs to the Medicaid program among patients from intervention clinics, as compared to patients from control clinics.

Hypothesis 2a: Expenditures attributed to external services will decrease for patients from intervention clinics, but these expenditures will remain the same or increase for patients in the control clinics.

Hypothesis 2b: Total Medicaid expenditures will decrease for patients from intervention clinics, while expenditures for patients from control clinics will remain the same or increase.

Aim 3: Study the change processes associated with APM implementation, including the organizational, workflow, and service delivery changes made in the Community Health Centers (CHCs) during and after APM implementation.

Hypothesis 3a: APM clinics will make fundamental pre-post changes in patterns of clinical care delivery and staff workflow.

Hypothesis 3b: There will be variability among the intervention clinics in what changes are successfully achieved, associated with vision, approach, strategic planning, and other clinic characteristics.

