on utilization of CHC services and other recommended care, and the resulting effect on external services utilization and overall cost of care. The primary independent variable is whether or not the patient was exposed to the APM by being a patient at an intervention vs. control site (an *enabling / hindering factor*). The *primary dependent variables* of utilization of internal / external services and quality of care delivered are based on (i) the Medicaid initial core sets of health quality measures for adults,^{43,44} and (ii) pediatric care quality measures developed by AHRQ's National Advisory Council Subcommittee on Children's Healthcare Quality Measures for Medicaid and CHIP Programs, pursuant to the Children's Health Insurance Program Reauthorization Act. We will select measures that are: 1) identified by Oregon's Medicaid program and/or those on the list of Clinical Quality Measures and other EHR incentive programs;^{45,46} 2) feasibly measured with EHR or Medicaid claims data (**our team has created methods for adapting quality measures based on claims data for use in OCHIN's EHR data^{47,48}**); 3) representative across age groups and gender; 4) representative of treatment levels (e.g., prevention, acute and chronic condition care); and 5) relevant to CHC populations. With guidance from an expert advisory group, we will select and define final specifications and modify them to accommodate calculation over the pre-post periods. Assessment of internal services utilization and quality can be done using OCHIN's EHR data; assessment of external services utilization will use EHR data linked with Medicaid administrative data.

Statistical analyses. We will conduct analyses at the clinic- and patient-level. The clinic-level analyses are typically performed in cluster-randomized trials, and the individual-level analyses are typically performed in observational studies in order to account for socio-demographic differences among clinics.

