Clinic-level: We will summarize baseline measures using descriptive statistics and data visualization methods (e.g., histograms, scatter plots) to assess how baseline data differs. To compare pre- and post-APM rates, we will assess data in pre- and post-APM time periods, using regression methods to estimate pre- vs. post-intervention change for each clinic. We will use a Generalized Estimating Equation (GEE) approach to adjust for serial correlation and other potential confounders. The pre- vs. post-APM changes will be calculated with GEE logit regression between intervention and control CHCs (DID analysis). Additional analyses to account for differences among APM phases and temporal inclusion may be used.

Patient-level: The primary independent variable is whether a patient belongs to an intervention or control CHC. Other covariates include predisposing factors and need for services. We will use GEE models^{49,50} which offer flexible regression modeling to accommodate different sources of correlations (serial, intra-clinic, and intra-family), categorical and continuous covariates, and fixed and time-dependent covariates. These methods offer a wide range of parametric distributions to model the dependent variables, including logistic regression (binary data), beta regression (percent data), Poisson regression (count data), and Gaussian regression (normally distributed data). For example, to assess a change in quality rates, a GEE logistic regression model can analyze quality of care received in pre- and post-APM periods as a function of whether a patient belongs to an intervention or control CHC and other possible confounders (e.g., predisposing factors; need for services). Serial, and intra-clinic correlations will be modeled, and empirical robust standard errors will be applied, to provide valid inference.⁵¹ As an exploratory secondary analysis, we will evaluate the impact of the APM intervention on total number of recommended services received. The distribution of the total services received will be examined first before selecting a specific model to use for the analysis. Analytic models will be refined through an iterative process, guided by the hypotheses, conceptual model, and preliminary analyses. If there are significant patient differences between the intervention and control sites, we may use propensity score methods in the analysis phase to reduce the observed bias and adjust for imbalances between intervention and control clinics.⁵²

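### The clinic-level DID names only a GEE logit, which does not suit visit counts or visit rates under Hypothesis 1a; the patient-level matching of family to data type should be extended to it

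*Combined protocol and SAP*

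**What the plan says.** - **Outcome.** Hypothesis 1a (Specific Aims) reads: "Patterns of internal services utilization (e.g., face-to-face visits, e-mail visits) will change" in intervention clinics, whereas for control clinics "patients' rates will not change". No unit, denominator or time window is given. Under Study variables, use of internal and external services is among the primary dependent variables.
- **Clinic-level model.** The Clinic-level paragraph of Statistical analyses begins generally, "using regression methods to estimate pre- vs. post-intervention change for each clinic", and adds GEE for serial correlation and confounding. It then specifies the comparison of intervention with control clinics: "The pre- vs. post-APM changes will be calculated with GEE logit regression between intervention and control CHCs (DID analysis". The sentence is not limited to quality measures and is not offered as an example.
- **Patient-level model.** The next paragraph lists families by type of data: "including logistic regression (binary data), beta regression (percent data), Poisson regression (count data), and Gaussian regression (normally distributed data". Its worked logistic example concerns quality of care. It also says that models will be refined iteratively.
- **Status of the two levels.** "We will conduct analyses at the clinic- and patient-level". Neither is named as primary. The Aims 1 and 2 Evaluation Summary table describes the clinic-level analysis only as DID and gives no link function.

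**The concern.** A logit models a mean that lies between 0 and 1. It suits quality measures, where each eligible patient either did or did not receive a service. It does not naturally suit visit volume, which can exceed one per patient in any reasonable window.

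Visit volume is not a side issue. The plan moves clinics from per-visit to capitated payment, and its Inclusion criteria section anticipates that face-to-face visits may fall as a result. An analyst who follows the clinic-level sentence for this outcome has three options: meet a model that will not fit, choose a time unit short enough to bring the rate below 1, or transform the outcome. The last two change what is estimated, and the choice could be made after the data have been seen.

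**Working it through.** The documents contain no visit rate, effect size, power or sample-size calculation, so there is no figure of the plan's to reproduce. Every numerical input below is an assumption. Only the choice of model comes from the plan.

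**1. The same change in different units.** Assume 3 visits per person-year before APM in both arms, a 10% fall in the intervention arm, and no change in the control arm. The DID rate ratio is then 0.90, with ln 0.9 = −0.105, whatever the unit. On the logit scale the DID odds ratio is [r₂/(1−r₂)] ÷ [r₁/(1−r₁)], where r₁ and r₂ are the intervention arm's rates before and after.

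| Unit | r₁ | r₂ = 0.9 r₁ | Odds ratio | Log odds ratio |
|---|---|---|---|---|
| Month (3/12) | 0.25 | 0.225 | (0.225/0.775)/(0.25/0.75) = 0.871 | −0.138 |
| Quarter (3/4) | 0.75 | 0.675 | (0.675/0.325)/(0.75/0.25) = 0.692 | −0.368 |
| Year | 3.0 | 2.7 | 3/(1−3) = −1.5, so no logit exists | – |

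**2. Simulated clinic-level GEE.** The set-up was 20 clinics (10 per arm), 24 periods (12 before, 12 after), exchangeable working correlation and a true rate ratio of 0.9. Each fit used its own random draw.

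| Mean rate per period | Binomial, logit | Poisson, log |
|---|---|---|
| 3 | no valid estimate, not converged | −0.107 |
| 0.25 | −0.131 (log odds ratio), converged | −0.105 |

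The log-link model recovers ln 0.9 = −0.105 at both levels. The logit fails above 1. Below 1 it converges, but to a different quantity, close to the −0.138 from the algebra in step 1.

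**3. One possible workaround: any visit, yes or no.** The plan does not state this; the step shows only what it would cost. Take a 10% fall in mean visits m, two-sided alpha 0.05, 80% power and a simple two-group comparison without clustering or DID.

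- P(any visit) = 1 − exp(−m) for Poisson (dispersion k = 0), or 1 − (1 + km)^(−1/k) for negative binomial. The sample size is the pooled-variance formula for two proportions.
- For the count model, n per arm = (1.96 + 0.84)² × [(1/m₁ + k) + (1/m₂ + k)] / (ln 0.9)².

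| m, k | Any visit, before to after | n per arm, any visit | n per arm, count | Ratio |
|---|---|---|---|---|
| 0.5, 0 | 39.3% to 36.2% | 3816 | 2986 | 1.28 |
| 2, 1 | 66.7% to 64.3% | 6259 | 2161 | 2.90 |
| 4, 0 | 98.2% to 97.3% | 4313 | 374 | 11.5 |

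Over m from 0.5 to 4 and k from 0 to 2, the ratio runs from about 1.3 to 11.5. The loss is modest when visits are rare and large when nearly everyone has at least one.

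**The case against.** The strongest reply is that this is a wording gap with limited consequences.

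- **The outcome is not defined as an unbounded rate.** Hypothesis 1a speaks of patterns and rates, some comparisons use patients with clinic contact as denominator, and final specifications are left to an expert advisory group. A share, such as the proportion of contacts that are face-to-face, is a proportion that a logit can fit. This stands. But visits per patient or per person-time is an ordinary reading of the hypothesis, and nothing in the plan excludes it.
- **A count model is already planned.** The patient-level list offers "Poisson regression (count data), and Gaussian regression (normally distributed data", with intra-clinic correlation and robust standard errors. This stands and limits the harm: Hypothesis 1a has one suitable analysis. It does not repair the clinic-level analysis, to which the plan also commits.
- **The model is not rigidly fixed.** The clinic-level paragraph first speaks of regression in general, and the plan allows iterative refinement. This stands in part. The general phrase describes change within each clinic, and the refinement sentence sits under Patient-level, so neither clearly overrides the logit sentence.

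A reader might infer more: that a logit cannot be fitted to visit data at all, or that the plan forces visits to be recoded as any versus none. The documents support neither. The rate unit is open, a logit fits shares and rates below 1, and no section proposes the recoding.

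**Conclusion.** The mismatch is real, and the clinic-level sentence should be changed. It names one model for the intervention-control contrast, and that model does not suit visit counts or visits per person-time, a plausible form of a main outcome. Above 1 there is no valid fit. Below 1 the result is an odds ratio whose size depends on an undefined time unit: 0.87 or 0.69 for the same 10% fall in the example.

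These sizes rest wholly on assumed rates, dispersion and effect. The sample-size ratios of 1.3 to 11.5 also ignore clustering and DID and describe a hypothetical recoding, so they are not an estimate of what this study would lose. The conclusion does not extend to quality measures or other proportions, where a logit is appropriate, or to the patient-level analysis.

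**What to change.** Replace the logit sentence in the Clinic-level paragraph with text such as:

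> Clinic-level DID will use a GEE with the family and link matched to the outcome: log link (Poisson or negative binomial) with a log person-time offset for visit counts and rates; logit (binomial with denominators) for quality measures and other proportions.

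Also state the denominator for visit rates, that is, whose person-time is counted and over what window.

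The cost is one replaced sentence and one definition. No new data are needed, and the change applies the plan's own patient-level principle to the clinic level. It should be made before outcome data are analysed, so that the choice of unit and model cannot be driven by the results.

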We will utilize a mixed-methods approach, drawing upon both qualitative and quantitative data from clinic site visits, clinic surveys, key informant interviews, follow-up calls, Medicaid administrative claims, and the OCHIN electronic health record (EHR).

Background and Significance:

The common practice of reimbursing primary care providers through a fee-for-service model hampers efforts to develop patient-centered medical homes: it rewards a high volume of face-to-face clinic visits, which does not necessarily lead to value, quality, and patient-centered care. This is especially problematic in Community Health Centers (CHCs), which are currently paid based on the Prospective Payment System (PPS) rate, a fee-for-service model. To reform this payment model in CHCs, Oregon developed an Alternative Payment Methodology (APM) that converts PPS (Medicaid revenue) to a prospective, capitated per-member per-month rate. The Oregon Primary Care Association (OPCA) is providing technical assistance to the APM clinics, with funding from the Robert Wood Johnson Foundation. The APM project seeks to (i) incentivize providing value over volume of visits, (ii) support comprehensive treatment modalities for patients with complex needs, and (iii) allow CHCs to focus more of their resources on population health initiatives.

APM is being implemented in several phases. Three CHC organizations are participating in Phase I of the APM demonstration project, which kicked off on March 1, 2013. Five additional CHC joined Phase II July 1, 2014 or October 1, 2014. Phase III began July 1, 2015 with three additional CHC organizations. Each CHC organization may include several clinics. All but one of the APM CHCs are members of the OCHIN community health information network practice-based research network, with a single, shared EHR. In this study, we propose to evaluate the APM clinics and/or patients matched to an equal number of control clinics and/or patients that are part of the OCHIN network.

Preliminary Studies / Progress Report:

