Analysis Plan. We will begin qualitative analyses shortly after data collection commences. The study team will meet regularly to review all data, and listen to and discuss key segments of the recorded interviews. Analyzing qualitative data as it is collected is crucial to monitoring data quality, refining observation and interview guides, and monitoring theme saturation. This ongoing process will be used to track emerging themes and create a coding template to be used for more in-depth analysis. We will follow the 5-phase analysis strategy described by Miller and Crabtree (describing, organizing, connecting, corroborating/ legitimizing, representing).^{34,35} We will use an immersion-crystallization approach in which the team reads and discusses the data for each clinic (immersion) to identify key findings (crystallization);^{35,36} we will do this twice, first to identify key themes within each “case” CHC, and then to identify cross-case finding.

The survey data and interview transcripts will be coded using the 5-phase analysis strategy explained above. We will also analyze differences between the Phase I and Phase II clinics’ experiences with APM implementation.

Quantitative data collection

We will compile EHR and Medicaid claims datasets that include data from up to 3 years pre-APM implementation, during implementation, and ≥ 3 years post.

Aims 1 and 2 Evaluation Summary				
Evaluate effect of APM intervention on:	Study Time Periods	Data Sources	Inclusion Criteria	Analyses
Aim 1. Internal services utilization and quality of care delivered; Aims 2 & 3. Utilization of and spending on services outside of the CHC,	Up to 3 years pre-APM implementation; ≥ 3 -years post-APM implementation;	1. Internal services: OCHIN EHR data 2. External services and expenditures:	1. Total clinic population: established patients at intervention and control clinics aged 2-64 2. Medicaid	Clinic level analysis using the DID analysis and patient level analysis using Generalized Estimating Equation models, to accommodate serial and intra-clinic correlations, categorical and continuous covariates, fixed and time-dependent covariates. Two-part models will be used to accommodate distributions

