total Medicaid spending.	(We will assess how long implementation takes and include it as transition time to our analyses)	OCHIN EHR data; Medicaid administrative data (including intervention CHCs' per-member per-month capitated payment rates)	Population: Medicaid-enrolled patients at intervention and control clinics aged 2-64	of healthcare spending. Matching methods will be utilized to reduce the observed bias and to adjust for imbalances between intervention and control clinics and/or patients.
--------------------------	--	--	--	--

Data Sources

EHR data. We will assemble a dataset of EHR data elements including all demographics, healthcare utilization, diagnoses, treatment, and health insurance coverage start and stop dates for all established patients age 2-64 for patients of APM clinics and their matched controls. We will include data from the following dates: no earlier than January 1, 2010 – December 31, 2018. The EHR is **centrally hosted and managed** at OCHIN and shared across all study CHC clinics. OCHIN maintains this central data warehouse, and the data are standardized across all OCHIN CHCs and regularly checked for accuracy.

Medicaid administrative data. These data will provide information on external services received and costs incurred. Oregon's Medicaid recipients are assigned unique individual identification (ID) numbers, facilitating data linkages across multiple databases, including the OCHIN EHR data. We will use claims and cost data from Medicaid.

Linkage between EHR and Medicaid administrative data. Project staff will use state ID numbers to create individual-level linkages between OCHIN EHR and Medicaid data.³⁷⁻³⁹ **All transfers will be done securely.** A de-identified dataset will be transferred to OHSU. The lead research analyst at OHSU has obtained security clearances to work with OCHIN's data team to assist with preparing the dataset to transfer to OHSU.

This study is being conducted in collaboration with OCHIN. The State of Oregon data will be shared with OCHIN under a Data Access Agreement. OCHIN will then share Medicaid and OCHIN EHR data with OHSU under a Data Use Agreement.

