Econometric analyses. Using difference-in-differences methods, we will calculate the average pre-post APM difference in spending of patients in APM intervention clinics, subtracted by the average difference among patients in comparison clinics. Changes in spending after APM implementation in the intervention

clinics vs. spending changes in the control clinics will “net out” any secular changes not related to APM. Any remaining significant differences in outcome – the DID – are attributed to the APM intervention. These findings will help to assess whether the APM intervention can help reduce costs, and if so, whether the reduction comes from lower spending at the CHC level or through reductions in potentially unnecessary or inefficient use of specialty and hospital services. We note that CHCs are not financially at risk for services outside of the CHC and thus do not have incentives to act as gatekeepers to care. Thus, reductions in spending for specialty services and other external services would most likely reflect improvements in internal care delivery.

Analytically, the difference-in-differences estimate is represented by the marginal effect on the interaction between a dummy variable indicating that the observations occur in the post-APM period and a dummy variable indicating the individual’s attribution to an APM intervention clinic. We will also include patient-level variables to account for predisposing factors and need for services. A variety of issues must be addressed in our DID estimation:

Definition of external services. External services will be defined as any care occurring outside of the CHC, e.g., emergency department visits, hospitalizations, and other ambulatory care that takes place in settings other than the CHC.

Accounting for clinic-level effects. Our study will focus on the “treatment-effect” of the APM: how does the transition to a capitated payment system affect health care spending? Since this is our main focus, our approach may include use of clinic-level fixed effects to net out any time-invariant differences in clinic-level cost outcomes. However, recognizing the potential interest in clinic-level effects, in secondary analyses we will test hierarchical (mixed) models to more specifically model (i) clinic-level variation and (ii) patient-level variation.

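### With four APM start dates, no defined post period for controls and optional phase adjustment, the main DID does not guarantee that a common secular trend cancels

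*Combined protocol and SAP*

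**What the plan says.** **Start dates.** Background and Significance gives four. Three organizations entered in Phase I (March 1, 2013) and three in Phase III (July 1, 2015). The middle phase has two dates of its own: "Five additional CHC joined Phase II July 1, 2014 or October 1, 2014".

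**Controls.** The same section has the APM clinics or patients "matched to an equal number of control clinics and/or patients that are part of the OCHIN network". No section says which date opens the post period for a control, that a control takes its partner's date, or that matched sets are kept in the analysis.

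**Windows.** Quantitative data collection plans "data from up to 3 years pre-APM implementation, during implementation, and ≥ 3 years post". Data Sources (EHR data) limits the extract to "no earlier than January 1, 2010 – December 31, 2018". The evaluation summary table adds a transition period whose length is still to be assessed. Nothing requires equal window lengths across phases.

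**Models.** Econometric analyses defines the spending DID as the interaction of an APM-clinic dummy with "a dummy variable indicating that the observations occur in the post-APM period". Statistical analyses (Clinic-level) compares pre-post change between APM and control clinics by GEE logit regression. Neither model names a phase or calendar-time term. On phase, the clinic-level paragraph says only: "Additional analyses to account for differences among APM phases and temporal inclusion may be used". Clinic fixed effects in the spending model are optional too.

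**Interpretation.** Econometric analyses states that the control comparison removes secular change unrelated to APM, and it attributes any significant remainder to APM.

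**The concern.** Pre and post cover different calendar spans in each phase. A single post indicator therefore makes each arm's change a weighted average of different secular changes, with weights set by that arm's mix of start dates. If the mixes differ, the two averages need not be equal even when trends are exactly parallel within every phase.

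The mixes could differ in two ways that the plan leaves open:
- Controls may not be given their match's start date. Until that date is defined, the control arm has no phase mix at all. This is the more basic gap.
- Clinics may be matched one to one but analysed with patients as the weights, so that panel size changes the phase shares.

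Any remainder would be read as an APM effect on use, quality or spending. Its sign would depend on which arm carries more of the early phase. Robust standard errors would not help, because this is bias and not variance.

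**Working it through.** The plan gives no bias, power or sample-size figure for the DID, so there is none to reproduce. The check takes a true APM effect of zero and one trend common to both arms.

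**Formula.** DID bias = sum over start dates of (APM-arm share − control-arm share) × D, where D is the change in the common trend from the pre to the post window for that start date.

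**Step 1: windows.** Take 36 months pre and all post data to December 31, 2018, which the plan permits. No transition period is modelled, because its length is not stated. The distance between window midpoints is 18 + (post months)/2.

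| Start date | Post months | Midpoint distance (months) | Years |
|---|---|---|---|
| March 1, 2013 | 70 | 53 | 4.42 |
| July 1, 2014 | 54 | 45 | 3.75 |
| October 1, 2014 | 51 | 43.5 | 3.63 |
| July 1, 2015 | 42 | 39 | 3.25 |

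Phase I and Phase III differ by 53 − 39 = 14 months.

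**Step 2: linear trend, unequal windows.** Assume the APM arm has 30 points more of its weight in Phase I and 30 points less in Phase III than the control arm, and a trend of 3 points per year. Bias = 0.30 × 14/12 × 3 = 1.05 points. Share differences of 10 to 40 points and trends of 1 to 4 points per year give 0.10 × 14/12 × 1 = 0.12 up to 0.40 × 14/12 × 4 = 1.87 points.

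**Step 3: linear trend, equal windows.** With 36 months each side, the midpoint distance is 36 months for every start date. The bias is then zero for any phase mix.

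**Step 4: a step in January 2014, assumed 10 points, same 30-point difference.**
- Post to December 2018: the step counts 60/70 = 0.857 in Phase I. In Phase III it counts 1 − 18/36 = 0.500. Bias = 0.30 × (0.857 − 0.500) × 10 = 1.07 points.
- 36 months each side: 26/36 = 0.722 against 0.500. Bias = 0.30 × 0.222 × 10 = 0.67 points.

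Equal windows therefore do not protect against a non-linear trend.

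**Step 5: controls not given their match's date.** Suppose every control used the Phase I date. Weight the APM arm by organizations (3, 5, 3), with the five in Phase II assumed split equally between its two dates. Its mean distance is (3 × 4.42 + 2.5 × 3.75 + 2.5 × 3.63 + 3 × 3.25)/11 = 3.77 years, against 4.42 for controls. The bias is −0.65 of one year's trend, or −1.95 points at 3 points per year. With equal 36-month windows and a linear trend it is again zero.

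**Step 6: logit scale.** Assume a 50% baseline, a true odds ratio of 1, and controls with 20 points more in Phase I and 20 fewer in Phase III. With the Step 1 windows, a trend of 0.1 logit per year gives an odds ratio of 0.975. With 36-month windows each side, that trend gives 0.9999, but a 0.5-logit step in January 2015 gives 1.05.

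**Step 7: remedies.** Least squares was run on noise-free clinic-months, with hypothetical clinic counts by start date of 6/5/5/6 (APM) and 10/5/5/2 (control), a linear trend and the Step 1 windows. The bias was −0.23 of a year's trend without clinic fixed effects and −0.21 with them. With phase-by-post terms, and each control on its phase's date, it was 0.000 for every trend and window tested. With the same mix in both arms it was 0.000 without any phase term.

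**The case against.** A reader might infer that a difference in phase mix alone leaves part of the secular trend in the DID by construction, even with inherited dates and parallel trends. The documents do not support that. Step 3 shows that a linear trend cancels for any mix when windows are equal. The plan permits equal 36-month windows, since even Phase III has 42 post months. The December 2018 limit is the span of the dataset and not a fixed analysis window.

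Nor do the documents show that the mix will differ. They allow one-to-one matching of patients as well as clinics. With inherited dates and equal weights, phase shares would be equal and any common trend would cancel. If the clinic-level analysis weights each clinic's change equally, panel size has no influence there.

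The plan also contains no full model equation, allows time-dependent covariates, and foresees phase differences. The fair charge is that the protection is not prespecified, not that it is ruled out.

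All of this stands, and it limits the point. It does not remove it. Equal windows, inherited dates and retained matched sets are all possible under the plan, but none is required. Equal windows do not deal with a step, and clinic fixed effects alone leave most of the remainder. The section on patient-level models also says that models will be refined iteratively, so an optional adjustment may be chosen after results are seen.

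**Conclusion.** The point holds in conditional form. As written, the main DID does not secure the removal of secular change that Econometric analyses claims for it. A common trend can leave a non-zero DID with no APM effect when two conditions hold together: the arms' phase weights differ, and either window lengths differ by phase or the trend is non-linear or a step. If either condition is absent, the trend cancels (on the logit scale almost exactly, in the case of unequal weights with equal windows and a linear trend).

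In the illustrations the remainder is about 0.7 to 1.1 points for a 30-point difference in mix, and about 2 points in size if all controls used the Phase I date with unequal windows. These sizes rest on assumed mixes and trends and on omitting the transition period. The documents give no clinic or patient counts by phase and no outcome trend, so the figures show scale and do not predict the study's bias. The plan should be changed, because the gap touches its central inference and is cheap to close.

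**What to change.** 1. Define the index date for controls: each takes the start date of its matched APM clinic or patient.
2. Within each start date, use the same calendar window in both arms, with the same handling of the transition period.
3. In the main GEE models and in the spending DID, replace the single post term with start-date-by-period terms for the four dates, and add phase-by-arm baseline terms.
4. Report the pooled APM-by-post effect from that model, with phase-specific effects beside it.
5. In the clinic-level paragraph, turn the optional phase and time analysis into a commitment.

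The cost is a short wording change and a few more model terms. The downside is the loss of a few degrees of freedom, with a limited number of clinics per phase. Phase-specific effects will be imprecise and should be read as supporting the pooled estimate.
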